6.2.1.2. Supplementary Analysis

This analysis is the same as the main analysis in [Section 6.2.1.1](#) except data from sibling(s) will be added to the data from the FAS if applicable. No graphics will be produced for this analysis.

Endpoints:

- Change from Baseline in percent normal mini-dystrophin expression level in biceps brachii muscle biopsies at Day 360 (Week 52) using an LC-MS assay (primary peptide is LLQV).
- Change from Baseline in percent normal mini-dystrophin expression level in biceps brachii muscle biopsies at Day 360 (Week 52) using an LC-MS assay (supplementary peptide is LEMP).
- Change from Baseline in percent of muscle fibers expressing mini-dystrophin in biceps brachii muscle biopsies at Day 360 (Week 52) as assessed by immunofluorescence.

Analysis:

- Estimand strategy: Secondary Estimand ([Section 2.2.2](#)).

- Analysis set: FAS (Section 4) plus data from sibling(s) (Section 2.3.3).
- Analysis methodology: Change from baseline will be analyzed using an ANCOVA model (Section 5.2.1.3) including terms for treatment group, and Screening age covariate (continuous variable).
- Intercurrent events and missing data: All available data in the reporting period will be included during the first 52 weeks. The intercurrent events and missing data will be handled as described in Section 2.2.2
- N, mean, SD, median, Q1, Q3, minimum, and maximum at Baseline and Day 360 (Week 52) for the observed value and change from baseline will be provided for fordadistrogene movaparvovec and placebo.
- The fordadistrogene movaparvovec and placebo LS means, standard error of each LS mean, and 95% CIs for the LS means along with the difference between the LS means (fordadistrogene movaparvovec minus placebo) and the corresponding standard error, two-sided p-value, and 95% CI at Day 360 (Week 52) will be provided.

6.2.2. Serum CK Concentration

Endpoint: Change from Baseline at Week 52 in serum CK concentration

Analysis:

- Estimand strategy: Secondary Estimand (Section 2.2.2).
- Analysis set: FAS (Section 4).
- Analysis methodology: Change from baseline will be analyzed using an MMRM approach for log transformed data (Section 5.2.1.2) including visits through Week 52 where serum CK concentration is assessed (ie, Weeks 1, 2, 5, 9, 13, 18, 35, 52) with additional fixed effects for natural log of Baseline serum CK concentration (continuous variable), Screening age covariate, and natural log of Baseline serum CK concentration by visit interaction, Screening age covariate by visit interaction.
- Intercurrent events and missing data: All available data in the reporting period will be included. The intercurrent events and missing data will be handled as described in Section 2.2.2
- N, mean, SD, median, Q1, Q3, minimum, and maximum at Baseline and all visits through Week 52 where serum CK concentration is assessed for observed serum CK concentration, changes from baseline, and percentage change from baseline will be provided for fordadistrogene movaparvovec and placebo.
- The fordadistrogene movaparvovec and placebo back-transformed LS means (ratio of geometric mean) and 95% CIs along with the back-transformed difference (i.e., ratio)

between the LS means (fordadistrogene movaparvovec – placebo) and the corresponding 95% CIs will be provided for change from Baseline in serum CK concentration for all visits through Week 52 where serum CK concentration is assessed. P-values from the log transformed analysis will be provided.

Graphical displays:

- The distribution of percentage change from Baseline in observed serum CK concentrations for fordadistrogene movaparvovec and placebo at each visit will be displayed graphically using box plots.
- The fordadistrogene movaparvovec and placebo back-transformed LS means and 95% CIs for each visit will be displayed graphically.

6.2.3. Number of Skills Gained and Skills Improved or Maintained based on the NSAA

Endpoints:

- Number of skills gained at Week 52 based on the individual items of the NSAA.
- Number of skills either improved or maintained at Week 52 based on the individual items of the NSAA.

6.2.3.1. Main Analysis

- Estimand strategy: Secondary Estimand ([Section 2.2.2](#)).
- Analysis set: FAS ([Section 4](#)).
- Analysis methodology: For each participant, the number of skills gained at Week 52 will be expressed as a proportion of the number of skills at Baseline that could be gained (numerator is the number of items on NSAA gained at Week 52 and denominator is number of items on NSAA with score 0 at baseline). The number of skills either improved or maintained at Week 52 will be expressed as a proportion of the number of items at Baseline that could be improved or maintained (numerator is the number of items on NSAA improved or maintained at Week 52 and denominator is number of items on NSAA which is 17). These proportions will be analyzed using a generalized mixed linear model with a Binomial distribution and logit link ([Section 5.2.3](#)) including terms for treatment group and Screening age covariate (continuous variable).
- Intercurrent events and missing data: All available data at Week 52 will be included. The intercurrent events and missing data will be handled as described in [Section 2.2.2](#).
- The number (%) of participants with 0, 1, 2, 3, etc. with skills gained and the number (%) of participants with 0, 1, 2, 3, etc. with skills improved/maintained as observed at Week 52 will be provided for fordadistrogene movaparvovec and placebo. The count of skills gained at Week 52 and count of skills either improved or maintained at Week

52 will be summarized by treatment group using descriptive statistics (including, N, mean, SD, median, Q1, Q3, minimum, and maximum).

Additionally, for the endpoint, number of skills gained, the number of skills that could be gained at Baseline (those with value 0 at Baseline) will be summarized for each treatment group and overall by descriptive statistics (including, N, mean, SD, median, Q1, Q3, minimum, and maximum).

- The fordadistrogene movaparvovec and placebo back-transformed LS means (ie, mean proportion of skills) and 95% CIs along with the back-transformed difference between the LS means (ie, ratio of mean proportions of skills) and 95% CI at Week 52 will be provided. Two-sided p-value will also be provided.
- An estimate of the mean number of skills gained at Week 52, based on the analysis model, can be derived by multiplying the proportion of skills gained (the back-transformed LS Mean) for each treatment group by the mean number of skills at Baseline that could be gained across all participants, irrespective of treatment group.

An estimate of the mean number of skills improved or maintained at Week 52, based on the analysis model, can be derived by multiplying the proportion of skills improved or maintained (the back-transformed LS Mean) for each treatment group by 17, which is the number of skills at Baseline that could be improved or maintained.

Graphical displays:

- The number (%) of participants with 0, 1, 2, 3, etc. skills gained at Week 52 will be displayed graphically in a bar chart with a bar for each treatment arm. Similarly, the number (%) of participants with 0, 1, 2, 3, etc. skills improved/maintained at Week 52 will be displayed graphically in a bar chart with a bar for each treatment arm.

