2.3.1. Sample Size Determination

The sample size of 99 participants in the FAS (see Section 4) is based on the primary efficacy endpoint of change from Baseline at Week 52 in the NSAA total score. The above sample size (assuming 3 participants will drop out of the study prior to Week 52) will provide 98% power to detect a treatment difference (fordadistrogene movaparvovec minus placebo) of 3.0. These calculations are based on $\alpha=0.05$ (two-sided), a 3-look group-sequential design with a gamma family (-1) spending function to determine the efficacy boundary, a gamma family (-4) spending function for the non-binding futility boundary, a common standard deviation of 3.5, and using the normal approximation of the test statistic for the comparison between two means.

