6.5.2. Baseline NSAA Total score

The following endpoints will be evaluated by Baseline NSAA total score strata:

- Change from Baseline at Week 52 in the NSAA total score
- Change from Baseline at Week 52 in the 10 meter run/walk test velocity.
- Change from Baseline at Week 52 in the rise from floor velocity.
- Baseline NSAA total score strata will be defined by the observed median of baseline NSAA total score based on all participants in the FAS during the reporting period. The 2 subgroups will be determined as below:
 1. < Median
 2. ≥ Median

Analysis:

- Analysis set: FAS ([Section 4](#)).
- Analysis methodology:

For each baseline NSAA total score strata separately, change from baseline will be analyzed using an MMRM approach ([Section 5.2.1.1](#)) including fixed effects for treatment group (categorical variable), visit (ordered categorical variable), and treatment group by visit interaction with additional fixed effects for screening age covariate (continuous variable) and screening age by visit interaction.

For each baseline NSAA total score strata, estimates of the mean changes from Baseline, standard error of each LS mean, and 95% confidence intervals for fordadistrogene movaparvovec and placebo will be provided for each visit along with the mean treatment group difference and the corresponding standard error, two-sided p-value, and two-sided 95% confidence interval for the mean difference at each visit.

- Intercurrent events and missing data: All available data in the reporting period will be included. The intercurrent events and missing data will be handled as described in [Section 2.2.1](#) and [Section 2.2.2](#) accordingly.
- For each baseline NSAA total score strata separately, the summary for each endpoint will be performed the same way as described in the corresponding main analysis in [Section 6.1](#) and [Section 6.2](#).

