Change from Baseline at Week 52 in the 10 meter run/walk velocity	Summary	FAS	All available data excluding the data from the particular rater(s) with potential data quality issues will be included Missing data will not be imputed	N/A
Change from Baseline at Week 52 in the 10 meter run/walk velocity	Sensitivity analysis Plot of LS means and 95% CIs	FAS	All available data excluding the data from the particular rater(s) with potential data quality issues will be included Missing data will not be explicitly imputed	MMRM with additional fixed effects for Baseline, Screening age covariate, Baseline by visit interaction, and Screening age covariate by visit interaction
Change from Baseline at Week 52 in the 10 meter run/walk velocity	Screening age strata subset Summary	FAS	All available data will be included Missing data will not be imputed	Not applicable (N/A)
Change from Baseline at Week 52 in the 10 meter run/walk velocity	Screening age strata subset	FAS	All available data will be included Missing data will not be explicitly imputed	For each Screening age strata separately, MMRM with additional fixed effects for Baseline NSAA total score, and Baseline NSAA total score by visit interaction.
Change from Baseline at Week 52 in the 10 meter run/walk velocity	Screening age strata subset The p-value for the Screening age strata interaction term	FAS	All available data will be included Missing data will not be explicitly imputed	NSAA main analysis (MMRM) subset on Screening age strata and MMRM with additional fixed effects for Baseline NSAA total score, Baseline NSAA total score by visit interaction, Screening age strata, Screening age strata by visit interaction, and Screening age strata by treatment group interaction.
Change from Baseline at Week 52 in the 10 meter run/walk velocity	Baseline NSAA total score subset Summary	FAS	All available data will be included Missing data will not be explicitly imputed	Not applicable (N/A)

Endpoint	Analysis Type	Population	Data Inclusion and Rules for Handling Intercurrent Events and Missing Data	Analysis Model

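### The 'improved or maintained' skills model omits baseline function, a strong predictor of the count, and has no dispersion term; the baseline-NSAA subgroup models and the Appendix 1 covariate for 10 meter velocity also need correcting

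*SAP*

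**What the plan says.** **Skills models.** SAP 6.2.3.1 analyses both skills counts as proportions with a binomial logit model "including terms for treatment group and Screening age covariate (continuous variable"). Appendix 1 and the sample code in Appendix 5.3 (written for skills gained) show the same two terms. For improved or maintained, the "denominator is number of items on NSAA which is 17" for every boy. Under SAP 3.2, an item at 0 at baseline counts only if it reaches 1 or 2. For skills gained, the denominator is the boy's own number of baseline zeros. SAP 5.1 places improved or maintained third, and skills gained fourth, among the alpha-controlled secondary endpoints.

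**Baseline-NSAA subgroups.** SAP 6.5.2 splits at the median baseline NSAA total and fits an MMRM in each half for NSAA total and the two velocities, "with additional fixed effects for screening age covariate (continuous variable) and screening age by visit interaction". No baseline term appears. The main models (6.1.1.1, 6.2.4.1), the age-strata models (6.5.1) and the region models (6.5.3) all keep baseline.

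**Appendix 1.** For 10 meter run/walk velocity by age stratum the table gives: "For each Screening age strata separately, MMRM with additional fixed effects for Baseline NSAA total score, and Baseline NSAA total score by visit interaction". The interaction row for that endpoint uses the same covariate. Section 6.5.1 and the rise-from-floor rows refer only to baseline.

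**The concern.** With the denominator fixed at 17 and an unchanged 0 scored as a failure, two boys with no change at all get different results solely because of where they started. Randomisation is 2:1 in about 99 boys and stratified only by age, so nothing balances baseline zeros between arms beyond chance. The endpoint is alpha-controlled, and a non-rejection stops formal testing of the fourth. Leaving baseline out also departs from the SAP's own practice for NSAA total, velocities, PODCI, CK, actigraphy and %pFVC, and no reason is given. For the biopsies, where baseline was removed, the version history gives one.

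In 6.5.2, a median split leaves spread within each half, and baseline NSAA total is not baseline velocity.

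**Working it through.** **1. The plan's own figure.** The SAP says "The sample size of 99 participants in the FAS", less 3 dropouts, "will provide 98% power to detect a treatment difference (fordadistrogene movaparvovec minus placebo) of 3.0", with "a common standard deviation of 3.5". For 64 against 32 boys, SE = 3.5 × √(1/64 + 1/32) = 0.758. Then 3.0/0.758 = 3.96, and Φ(3.96 − 1.96) = 97.7%. With all 99 boys it is 98.0%, and with the three-look boundaries 97.0%. The stated 98% is reproduced within about a point. The SAP gives no power or precision for the skills or subgroup models.

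**2. The endpoint by definition.** A boy with five baseline zeros and no change scores (17 − 5)/17 = 12/17. A boy with no zeros and no change scores 17/17.

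**3. Simulation, improved or maintained.** From the SAP: 99 boys, 2:1, 17 items, the success rule, and the binomial logit model. Assumed, because the SAP gives none:
- item success 0.30 (from 0), 0.90 (from 1) and 0.85 (from 2);
- mean (SD) of baseline zeros 2.2 (1.8), 3.7 (3.0) or 4.9 (4.0);
- between-boy SD on the logit scale 0, 0.5 or 0.8;
- 1,500 trials per setting, fitted as events/trials.

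Results under no treatment effect at the widest spread of zeros, without / with the zero count as covariate:

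| Between-boy SD | R² of zero count | Empirical SE | Ratio | Model SE | Type I error |
|---|---|---|---|---|---|
| 0 | 0.66 | 0.160 / 0.104 | 1.54 | 0.114 / 0.120 | 16.1% / 2.3% |
| 0.5 | 0.53 | 0.173 / 0.128 | 1.35 | 0.114 / 0.119 | 20.3% / 6.6% |
| 0.8 | 0.39 | 0.191 / 0.159 | 1.20 | 0.113 / 0.118 | 23.5% / 15.1% |

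In the middle setting (zero SD 3.0, between-boy SD 0.5) the empirical SE was 0.165 / 0.136 (ratio 1.21) and the model SE 0.119 / 0.123. Over all settings R² was 0.13 to 0.66, the SE ratio 1.03 to 1.54, and type I error 6.8–23.5% / 2.3–16.3%.

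The model SE hardly moves because a pure binomial variance is set by the fitted mean and has no residual scale. Extra variation left by the missing covariate is therefore not reported.

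**4. Power.** At a per-item log odds ratio of 0.5, the planned model's rejection rate in the three tabulated settings went from 75.5 to 88.5%, 76.3 to 84.6% and 70.4 to 76.5%. The first figure of each pair comes from a test whose true size is 16 to 24%, so it is not power at 5%. With milder inputs (64 against 32, mean 2.5 zeros with SD 1 or 2, logit SD 0.7, item success 0.30 or 0.88, log odds ratio 0.6) it moved only from 84 to 85% and from 81 to 84%. With a dispersion-scaled SE, power in the middle setting of step 3 rose from 53 to 76% (all settings: 39–75% without, 56–92% with).

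**5. Skills gained.** Adding baseline NSAA left the empirical SE unchanged (0.276 without, 0.280 with), assuming the chance of gaining a skill does not depend on baseline total.

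**6. Subgroups in 6.5.2.** Omitting a covariate with correlation r to the change inflates the SE by 1/√(1 − r²). For velocity, if its baseline is unrelated to the stratifier, r = 0.2 gives 1/√0.96 = 1.02 and r = 0.6 gives 1/√0.64 = 1.25. For NSAA total the split leaves 1 − 2/π = 0.363 of the baseline variance under normality, so the within-half r² is 0.363r²/(0.363r² + 1 − r²). That is 0.015 at r = 0.2 and 0.170 at r = 0.6, giving factors of 1.01 and 1.10. The range of r is assumed.

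**7. Appendix 1.** Section 6.5.1 gives one model description for all four change endpoints and names baseline. The rise-from-floor rows agree; the 10 meter rows do not. No assumption is needed.

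**The case against.** Covariate choice in a randomised comparison is partly a matter of design, and chance imbalance is not bias. That stands: this is a point about efficiency and error rate. SAP 5.2.3 also speaks of a generalized mixed model, which might suggest a participant effect. But it names only fixed effects, Appendix 1 calls the model a generalized linear one, and the sample code has neither a random nor a scale statement.

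A reader might infer that the count is largely fixed at baseline. An R² of 0.13 to 0.66 supports this only at the upper end. A reader might also infer that both skills models lose precision. Skills gained already conditions on the zeros through its denominator, and no gain was seen. Or a reader might take the main harm to be lost power at the third endpoint, blocking the fourth. The large power gains belong to a dispersion-scaled fit that the SAP does not plan. In the planned model, fitted as events/trials, the clearer effect is an understated SE.

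In 6.5.2, dropping the stratifier for NSAA total parallels 6.5.1, which drops continuous age within age strata. The loss is small and outside alpha control. The velocity endpoints have the better case.

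**Conclusion.** The concern holds for improved or maintained. Its definition makes the baseline zero count a strong predictor, and the model ignores it. Under the assumed inputs this count explains roughly 10 to 65% of the variance, and omission makes the true SE about 3 to 50% larger. In the planned model this appears mainly as type I error above 5% on an alpha-controlled endpoint. Adding baseline alone does not fully restore the error rate where boys differ in other ways (up to 16.3%).

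The error rates assume events/trials fitting. The sample code enters a proportion without a trial count. If each boy were weighted as one trial, the SE would be about √17 = 4.1 times as large and the test would almost never reject. All sizes depend on item distributions that the SAP does not give; the direction follows from the endpoint definition.

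The 6.5.2 omission is real but modest: about 1 to 10% in SE for NSAA total and up to 2 to 25% for velocities. The Appendix 1 inconsistency is certain and editorial.

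**What to change.** Before unblinding:
- In 6.2.3.1, Appendix 1 and the sample code, add the baseline number of items scored 0 (or baseline NSAA total) to the improved-or-maintained model, with an overdispersion or participant-level term. State the fit as events out of 17.
- Leave the skills-gained covariates as they are on this ground.
- In 6.5.2 and its Appendix 1 rows, add the endpoint's own baseline and baseline-by-visit interaction, as in 6.5.3.
- In Appendix 1, change both 10 meter run/walk age-strata model rows from baseline NSAA total score to baseline velocity.

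The cost is SAP wording and code; the data are already collected. The improved-or-maintained odds ratio becomes conditional on baseline, and the conversion of LS means to a count out of 17 is taken at mean baseline. The SAP should say so.

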2.2.2. Secondary Estimand(s)

- Population: Boys with a genetic diagnosis of DMD who are ambulatory and age ≥ 4 to < 8 years;
- Variable: Each secondary endpoint;

- Intercurrent event(s) and missing data: The potential intercurrent events are death and loss of ambulation. The intercurrent events and missing data will be handled as described below:
 - Loss of ambulation or death: secondary endpoints related to NSAA scores for individual skills (i.e., 10 meter run/walk velocity, rise from floor velocity, number of skills either improved or maintained, and number of skills gained) will be set to 0 for all scheduled study visits after death. For participants with LOA, if the NSAA test is done post LOA, then the individual items from that assessment would be used in analyzing the secondary endpoints. A value of 0 would be assumed for the 17 NSAA items and the 2 velocity assessments only if the NSAA test is NOT DONE post a LOA.
 - Discontinuation from Study: missing data from visits after a participant discontinues from the study (with the exception of death) will not be explicitly imputed.
 - Missing data from a participant not being able to perform the NSAA due to acute illness or injury, will not be explicitly imputed.
 - For all other secondary endpoints (i.e., mini-dystrophin, CK concentration, PODCI), missing data will not be explicitly imputed regardless of the causes.
- Population-level summary: difference in means between fordadistrogene movaparvovec and placebo for each secondary endpoint.

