5.2.3. Analyses for Proportions based on Number of Successes

Endpoints defined as the number of successes out of a possible number of tests for each participant at each timepoint will be analyzed using a generalized mixed model assuming a Binomial distribution with a logit link. For example, for the number of skills gained in the NSAA, the endpoint is the number of skills gained out of the number of skills that can be gained (score 0 at Baseline). The maximum likelihood estimation method with Newton Raphson iteration will be used. The fixed effect of treatment group (as a categorical variable) will be included in the model along with any covariates given in [Section 6](#). The effect of

treatment will be examined using the Wald chi-square statistic (CHISQ option). LS means and 95% CIs and the difference in LS means and 95% CIs will be estimated using the z-statistic, by defining degrees of freedom to be infinite in the model (DDFM=NONE). The inverse link transform (ILINK) will be applied to obtain the LS means on the original scale, which will represent average proportions of success.

The estimate of difference in LS means when back-transformed will represent an odds ratio comparing the odds of a success occurring between two treatment groups. In order to represent these proportions as meaningful counts of success, the proportions will be multiplied by the average of the baseline values of the number of tests across all participants, irrespective of treatment group. For example, for number of skills gained, the average baseline number of skills that can be gained will be calculated. Then the back-transformed LS means representing the proportion of successes for each treatment group will be multiplied by this average baseline value, to give a representation of the average number of skills gained for each treatment group, for the population in this study.

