Appendix 5.3. Sample SAS Code for the Number of Skills Gained at Week 52 Analysis

```
/*save overall baseline mean as variable base_mean*/

proc sql;

  select avg(denomi) into: base_mean

  from adrs2 where ^missing(TRT01P);

Quit;

%put &base_mean;

proc glimmix data=adrs2;

  class TRT01P;

  model prop_skills = TRT01P agemodel / dist=bin link=logit chisq ddfm=NONE;

  lsmeans TRT01P / cl ilink ;

  lsmeans TRT01P / at agemodel=4 cl ilink ;

  lsmeans TRT01P / at agemodel=5 cl ilink ;
```

```

lsmeans TRT01P / at agetmodel=6 cl ilink ;
lsmeans TRT01P / at agetmodel=7 cl ilink ;
estimate 'Treat diff' TRT01P 1 -1 / cl ilink;
ods output LSMMeans=means4 estimates=est4;

run;

```

```

Data means5;

set means4 ;

extimate _MU_Gained=(MU)*&base_mean;

if agetmodel ^in (4, 5, 6, 7) & ^missing(TRT01P);

run;

```

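### Section 6.2.3.1 labels an odds ratio as a ratio of proportions for the two NSAA skills endpoints, and the sample code back-transforms the treatment contrast to neither

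*SAP*

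**What the plan says.** Both skills endpoints are analysed as proportions per participant. SAP Section 6.2.3.1 specifies a "generalized mixed linear model with a Binomial distribution and logit link" and refers to Section 5.2.3 for the method. Its reporting bullet then describes the between-group effect as the "back-transformed difference between the LS means (ie, ratio of mean proportions of skills"), with a 95% CI.

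Section 5.2.3 names the same quantity differently: "The estimate of difference in LS means when back-transformed will represent an odds ratio". It assigns the inverse link to the arm-level estimates only: "The inverse link transform (ILINK) will be applied to obtain the LS means on the original scale".

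Appendix 5.3 gives sample code for skills gained. The model line is "model prop_skills = TRT01P agemodel / dist=bin link=logit chisq ddfm=NONE", and the treatment contrast is "estimate 'Treat diff' TRT01P 1 -1 / cl ilink". The estimates table is saved whole, and the one later data step works on the LS means, not on the contrast. Appendix 1 lists a back-transformed difference with its CI for these endpoints but does not name the scale.

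The secondary estimand in Section 2.2.2 has one line for all secondary endpoints: "Population-level summary: difference in means between fordadistrogene movaparvovec and placebo for each secondary endpoint".

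**The concern.** Sections 5.2.3 and 6.2.3.1 describe the same output under the same link, and both descriptions cannot be right. An odds ratio and a ratio of proportions share the null value 1 but can differ greatly in size. An odds ratio printed under the Section 6.2.3.1 label would overstate the gain in skills, most of all where proportions are high. The sample code fits neither description, because the inverse link is meant for an arm's logit and not for a difference of two logits.

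Both endpoints are in the fixed testing sequence of Section 5.1, so their effect estimates and intervals will be read as confirmatory results if the sequence reaches them.

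**Working it through.** The SAP states no expected effect for these endpoints, so there is no figure to reproduce. The check is algebraic. The proportions used are assumptions that show the range.

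**Inputs.** Logit link (Sections 5.2.3 and 6.2.3.1, Appendix 5.3); inverse link applied to the contrast (Appendix 5.3); 17 items as the denominator for improved or maintained (Section 6.2.3.1).

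**Formulas.** Let p_T and p_C be the back-transformed LS means on active and placebo.

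- Contrast: d = logit(p_T) − logit(p_C) = log OR.
- Exponentiated: exp(d) = [p_T/(1−p_T)] / [p_C/(1−p_C)] = OR. This is what Section 5.2.3 describes.
- Ratio of proportions: p_T/p_C. This equals exp(d) only if the link is log.
- Inverse link of the contrast: exp(d)/(1+exp(d)) = OR/(1+OR). This is what the code's back-transformed column holds.

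**No effect.** d = 0 gives OR = 1, ratio = 1 and inverse link = 1/(1+1) = 0.5, whatever the placebo proportion.

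**One case in full (assumed 0.90 vs 0.80).** The odds are 0.90/0.10 = 9 and 0.80/0.20 = 4. So OR = 9/4 = 2.25, ratio = 0.90/0.80 = 1.125, and inverse link = 2.25/3.25 = 0.692. In counts out of 17 this is 15.3 against 13.6, a difference of 1.7 skills.

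| Assumed p_T vs p_C | Odds ratio | Ratio of proportions | Inverse link of contrast |
|---|---|---|---|
| 0.30 vs 0.30 | 1.00 | 1.00 | 0.500 |
| 0.20 vs 0.10 | 2.25 | 2.00 | 0.692 |
| 0.45 vs 0.30 | 1.91 | 1.50 | 0.656 |
| 0.90 vs 0.85 | 1.59 | 1.06 | 0.614 |
| 0.90 vs 0.80 | 2.25 | 1.125 | 0.692 |

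The second and last rows have the same odds ratio. At low proportions the wrong label does modest harm (2.25 against 2.00). At high proportions a 12.5% relative gain would be labelled as a 2.25-fold one.

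**Check by simulation.** A binomial-logit model was fitted to 500 null data sets (assumed 64 and 32 participants, 1 to 8 items each, age as covariate). The median odds ratio was 0.996, the median ratio of proportions 0.997 and the median inverse-linked contrast 0.499.

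**The case against.** The strongest reply is that Section 6.2.3.1 refers to Section 5.2.3, which has the scale right. On that view the parenthesis is one stale label. The amendment history in Appendix 6 records a change from log to logit link in version 8, which would explain it. That is a likely origin, but the label stands in the current analysis section and is wrong there.

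Three stronger readings are tempting, and the SAP does not support them.

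- **A reader might infer that the trial would report 0.5 for no effect, or show a benefit as harm.** The contrast output also holds the untransformed log odds ratio and its limits, and no step selects the inverse-linked column for reporting. A wrong-direction reading would need both that column and the stale label. Each arm's back-transformed mean, reported beside the contrast, would contradict it. The code is also headed as a sample and titled for skills gained only. Its use for improved or maintained is an inference from the shared method.
- **A reader might infer that error control for the two endpoints is compromised.** It is not. Section 5.2.3 tests treatment with a Wald chi-square on the logit scale, and no choice of back-transformation changes that p-value.
- **A reader might count the estimand's difference in means as a further rival definition.** It is one generic line that also covers CK, which Section 6.2.2 reports as a ratio. It is a loose fit to the skills analysis rather than a competing specification.

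**Conclusion.** The point holds as a reporting fault. Section 6.2.3.1 gives the wrong name to the between-group effect for two endpoints in the testing sequence, and the sample code for one of them back-transforms the contrast to a quantity that is neither an odds ratio nor a ratio of proportions. The algebra needs no assumption beyond the stated logit link.

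The size of the mislabelling does rest on an assumption, because the SAP gives no expected proportions. It is small when few skills are expected to count as successes and large when most are. High proportions seem more likely for improved or maintained, whose denominator is all 17 items. Hypothesis tests, p-values and the order of testing stand as planned.

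**What to change.** 1. In Section 6.2.3.1, replace the parenthetical ratio label with odds ratio, so that it agrees with Section 5.2.3.
2. In Appendix 1, name the odds ratio as the scale of the back-transformed difference for both skills endpoints.
3. In Appendix 5.3, replace `ilink` with `exp` on the ESTIMATE statement, and keep `ilink` on the LSMEANS statements, where it is correct. State that the same code pattern serves both endpoints, if that is intended.
4. Optionally, report the difference in model-based mean number of skills: (p_T − p_C) times the baseline mean number of items that could be gained, or times 17 for improved or maintained, with a delta-method CI. Section 6.2.3.1 already derives each arm's mean count, so only the difference and its interval are new. This would match the estimand's summary measure and is easier to read than an odds ratio.

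Items 1 to 3 cost two wording changes and one option in the code. Item 4 adds a short derivation. None of them changes the model, the test or the sample size.
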